The NCI-AACR Cancer Patient Tobacco Use Assessment Task Force developed the Cancer Patient Tobacco Use^{1–4,13,14} Questionnaire (C-TUQ). We propose that administering selected C-TUQ items to participants enrolling in 8 Phase II and Phase III ECOG ACRIN (EA) therapeutic trials will add value to parent trial research questions by advancing the field. Specifically, among patients with varied cancers (tobacco-related and non-tobacco-related) and cancer treatments, we will administer C-TUQ questions at EA trial enrollment and 3 and 6 months follow-up.

We have the following aims:

- a) **Treatment toxicity:** To determine the effects of tobacco, operationalized as combustible tobacco (1a), other forms of tobacco (1b), and environmental

tobacco exposure (ETS) (1c) on provider-reported cancer-treatment toxicity (adverse events (both clinical and hematologic) and dose modifications).

- b) **Symptom burden:** To determine the effects of tobacco on patient-reported physical symptoms and psychological symptoms.
- c) **Cessation patterns and treatment:** To examine quitting behaviors and behavioral counseling/support and cessation medication utilization.
- d) **Trial outcomes:** To explore the effect of tobacco use and exposure on treatment duration and relative dose intensity, and on therapeutic benefit, of 8 selected EA trials.

The findings will advance the nascent field of tobacco use in the context of cancer care by: 1) longitudinal assessment of cigarette smoking, other forms of tobacco use and secondhand smoke exposure at trial enrollment and at 3 and 6 month follow-up; 2) increase knowledge about the effects of tobacco use and exposure on treatment toxicity, physical and psychological symptoms and 3) oncology provider delivery, and 4) patient's perceptions of stigma and utilization of behavioral and pharmacological treatment of tobacco dependence. Finally, the use of this assessment would provide a unique additional value to the hypothesis of this trial, by allowing investigation of previously unanswered questions about the effects of tobacco use and exposure on trial adherence and outcomes among patients with smoking-related and non-smoking related cancers.

Rev. 6/16
Rev. 9/17

2. Objectives

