Sociodemographic Variables. Sociodemographic variables, including age, sex, zip code, and race/ethnicity are collected for all NCTN trial participants at registration. At baseline, participants will provide information on marital status (Q20 in Baseline STU) and education level (Q21 in Baseline STU) as part of the tobacco supplemental assessment.

Cancer Treatment Variables. Clinical variables including date of diagnosis, malignancy type (smoking related vs. non-smoking related, cancer stage), and treatment details (i.e. types and dates of surgery, chemotherapy, and/or radiation received), along with disease status and survival, will be captured in Medidata Rave via the parent protocol and will be available for analysis of the ancillary. Provider-assessed adverse events will also be captured via the parent protocol in Medidata Rave, using case report forms commonly used across the NCTN and using standard data elements.

Assessments

All items in Survey of Tobacco Use will be administered using the EASEE-PRO system. The advantage of our virtual electronic data capture system is that our proposed assessments will not be limited to, or dependent upon, patient trial visits. Confidential and potentially stigmatizing information can be provided without requiring direct contact with the care team.

Timing of Assessments

Given the critical questions that remain¹³ about the timing of conducting tobacco use assessments, we have carefully chosen to collect tobacco assessment data at trial enrollment, 3 and 6 month follow-up. For tobacco treatment trials, 6 month follow-up is the recommended primary outcome time point. By 6 month follow-up, most cancer treatment-related quitting activity⁶², cancer treatment initiation of therapy, and FDA-approved smoking cessation medication regimens will be completed. Adverse events during treatment will have been observed.

Statistical Considerations and Analysis Plans

The analysis plans described below are planned for a combined analysis of the data from the 8 selected ECOG-ACRIN trials. Consistency in the effects over the studies would be examined in this analysis.

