1. CHANGES IN SMOKING STATUS AND EXPOSURE. At baseline, combustible tobacco use (1a) will be characterized by smoking status (never smoker, former smoker, and current smoker based on Baseline STU Qs 1 and 5), other forms of tobacco use (1b) will be a composite variable determined by non-cigarette items (based on Baseline STU Q7 and Q14), and environmental tobacco smoke (ETS) level (1c) will be determined by current household and work exposure (Baseline STU Qs 15-16). At follow-up, combustible tobacco use (1a) will be examined by smoking status (Follow-up STU Qs 1 and 2), other forms of tobacco use (1b) will be determined by Follow-up STU Q10, and ETS level (1c) will be determined by 30 day household and work exposure (Follow-up STU Qs 11-12). We will examine tobacco use at baseline, 3 and 6 month follow-up, and change in status (abstinence in combustible tobacco, abstinence of other forms of tobacco use, and change

- in exposure to smoke-free home and work) using summary statistics (frequency and proportion). We will explore the effects of sociodemographic and cancer treatment factors on smoking status using logistic regression (comparing smokers and non-smokers). We will also evaluate factors associated with changes in smoking status.
2. **TREATMENT TOXICITY.** The selected trials capture information about adverse events during treatment using NCI's Common Terminology Criteria for Adverse Events, Version 4. Toxicities are measured at each treatment visit and graded according to severity, with grade 1 corresponding to mild toxicity and grade 5 signifying a lethal adverse event. We will determine each patient's worst degree toxicity across all event types and treatment visits and will compare the distribution of worst degree grades between smokers and non-smokers and between patients with environmental tobacco exposure and those without exposure using exact tests. We will also examine the distribution of worst degree grades between users with different form of tobacco use. In addition, we will explore the effects of tobacco use on dose modifications (yes vs. no) using logistic regression, with each patient's dose modification status determined across all treatment visits.

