 5. **TRIAL OUTCOMES.** We will compare treatment duration between smokers and non-smokers and between patients with environmental tobacco exposure and those without exposure. Cumulative incidence/competing risk methods will be used to estimate time to treatment discontinuation for adverse events, disease progression, completion per protocol, or other causes. Gray's test will be used to test for differences in the cumulative incidence distributions.⁷⁸ Differences in the distribution of reasons for discontinuation of treatment will be examined using exact tests. Relative dose intensity is defined as the ratio of actually delivered dose intensity to the planned dose intensity. The effects of tobacco use and

exposure on relative dose intensity ($\geq 90\%$ vs. $< 90\%$) will be explored using logistic regression. Differences in the primary endpoint and important secondary endpoints will be examined using log rank test and exact test (as appropriate).

Data collected in the tobacco use project will support a range of analyses. Precise estimates of power will depend on the prevalence of smoking at baseline among study participants, the proportion whose smoking status changes, and the duration and adequacy of follow-up.

References

1. Yi, Yang P, Parkinson J, Zhao X, Wampfler JA, Ebbert JO, Sloan JA. The relationship between cigarette smoking and quality of life after lung cancer diagnosis. *Chest*. 2004; 126(6):1733-1741. doi: 10.1378/chest.126.6.1733.
2. Gritz E. Rationale for Treating Tobacco Dependence in the Cancer Setting. Conference presentation at: Treating Tobacco Dependence at the National Cancer Institute's Cancer Centers. December 2009.
6. Dresler CM. Is it more important to quit smoking than which chemotherapy is used? *Lung Cancer*. 2003;39(2): 119-124.

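### The tobacco ancillary pools eight trials of different cancers and regimens, but its toxicity, dose and discontinuation comparisons are not stratified or adjusted by parent trial

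*Combined protocol and SAP*

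**What the plan says.** Section 9.6.3 refers the reader to Appendix VI for the tobacco statistics. There, "The analysis plans described below are planned for a combined analysis of the data from the 8 selected ECOG-ACRIN trials". Section 1.9 describes the setting as "among patients with varied cancers (tobacco-related and non-tobacco-related) and cancer treatments".

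The comparisons named in Appendix VI are:

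- **Item 2, toxicity.** The investigators "will compare the distribution of worst degree grades between smokers and non-smokers". Patients exposed to second-hand smoke are set against unexposed patients in the same way, and both contrasts rely on exact tests. Dose modification (yes/no) is related to tobacco use by logistic regression.
- **Item 5, treatment duration and dose.** Time to discontinuation by cause is estimated by cumulative incidence, and Gray's "test will be used to test for differences in the cumulative incidence distributions". Reasons for stopping are compared by exact tests. Relative dose intensity, split at 90%, is analysed by logistic regression.
- **Item 5, trial endpoints.** "Differences in the primary endpoint and important secondary endpoints will be examined using log rank test and exact test (as appropriate".

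None of these names parent trial, cancer type or regimen as a stratum or covariate. The only sentence about differences between trials is "Consistency in the effects over the studies would be examined in this analysis". By contrast, the models for smoking status (item 1) and symptom burden (item 3) do bring in cancer treatment factors, and Section 9.4 specifies stratified log-rank tests for this trial's own efficacy endpoints.

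**The concern.** Objectives 2.5.1 and 2.5.4 ask for the effect of tobacco on toxicity, dose intensity, treatment duration and benefit. Pooling tobacco-related and other cancers makes it plausible that smoking prevalence differs by trial. Pooling different regimens makes it plausible that toxicity and time on treatment differ too. If the two move together across trials, parent trial is a confounder, and a pooled comparison attributes trial differences to tobacco.

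Treatment duration is particularly exposed. Completion of planned therapy is one of the causes in the cumulative-incidence analysis, and its timing follows from the regimen's planned length: in this trial, 12 weeks for platinum and 18 for capecitabine (Section 5.1).

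**Working it through.** **The plan's own figure.** The only power statement in the ancillary (item 3) is 83% for a 2.5-point difference, SD 4.08, 26 against 230 patients, 5% type I error (taken as two-sided).

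- Group total: 1500 × 0.20 × 0.85 = 255, against 26 + 230 = 256.
- Standardised difference: 2.5 / [4.08 × √(1/26 + 1/230)] = 2.96.
- Power: Φ(2.96 − 1.96) = 84.2% by normal approximation, and 83.9% by the noncentral t.

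The figure reproduces. It treats the pooled data as one sample and has no bearing on confounding by trial.

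**Inputs for the illustration.** From Appendix VI: 1,500 patients, 20% smokers (300 smokers, 1,200 non-smokers), eight trials. Assumed, because the documents give no trial-level rates: equal-sized trials, four with lower and four with higher smoking prevalence *s* and grade 3+ rate *t*, and no smoking effect within any trial.

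**Spurious difference.** For equal-sized trials, with s̄ the overall prevalence,

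smokers minus non-smokers = Cov(s, t) / [s̄(1 − s̄)].

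For smoking 10%/30% and toxicity 40%/60%: 0.10 × 0.10 / (0.20 × 0.80) = 6.25 points.

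By direct count with two blocks of 750:

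- smokers: (75 × 0.4 + 225 × 0.6) / 300 = 55.0%
- non-smokers: (675 × 0.4 + 525 × 0.6) / 1200 = 48.75%

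**Rejection rate.** SE = √[0.5 × 0.5 × (1/300 + 1/1200)] = 0.0323, so z = 0.0625 / 0.0323 = 1.94. The two-sided rejection probability is Φ(z − 1.96) + Φ(−z − 1.96) = 49%.

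**Simulation.** 5,000 runs per setting with eight trials compared a pooled Fisher exact test with a Mantel-Haenszel test stratified by trial. Simulation error at a true 5% is √(0.05 × 0.95 / 5000) = 0.3 points.

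| Smoking | Grade 3+ | Spurious difference (points) | Pooled test rejects | Stratified test rejects |
|---|---|---|---|---|
| 20% in all | 40%/60% | 0 | 4.2% | 5.0% |
| 15%/25% | 45%/55% | 1.6 | 7.0% | 5.4% |
| 15%/25% | 40%/60% | 3.1 | 15.5% | 5.1% |
| 10%/30% | 45%/55% | 3.1 | 15.5% | 5.4% |
| 10%/30% | 40%/60% | 6.25 | 48.5% | 5.3% |
| 10%/30% | 30%/70% | 12.5 | 97.1% | 5.1% |

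The formula shows the condition: bias needs prevalence and event rate to be associated across trials. If either is constant, or if they vary without association, the covariance is zero and so is the spurious difference.

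**The case against.** **Silence is not a decision.** Appendix VI names families of tests without listing strata and never says the tests are unstratified. A reader might infer that adjustment was ruled out, and the text does not go that far. It remains true that someone following it would run plain pooled tests, and that the document specifies stratification or treatment factors elsewhere when it intends them.

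**The consistency check.** Looking across studies needs study-level estimates, which could expose an artefact. That is a real safeguard, but it concerns heterogeneity of effect. In the illustration the within-trial effect is zero everywhere, so it is perfectly consistent, and the pooled test still rejects too often.

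**Endpoint tests.** A reader might infer a single pooled log-rank test of the primary endpoint. The parent trials are Phase II and III studies of varied cancers, and choosing the test as appropriate is compatible with testing each trial's endpoint separately. This part of the point is therefore conditional on pooling.

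**Treatment arm.** It is tempting to call arm a second confounder. This trial randomizes 1:1, so smoking is balanced by arm in expectation, and the documents do not describe the other seven designs. Arm is not shown to confound.

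**Symptom burden.** The item 3 mixed models already include cancer treatment factors, and Appendix VI counts malignancy type and treatment details among the cancer treatment variables. The criticism is not extended to them.

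**Stakes.** Section 2.5 labels the objectives exploratory and ancillary and keeps these data out of this trial's clinical study report. That stands, and it limits the severity.

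**Conclusion.** The point holds for worst toxicity grade, discontinuation, dose modification and relative dose intensity, and for the endpoint tests if they are pooled. As specified, these comparisons can show a tobacco effect where none exists in any trial.

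The size depends on rates that the documents do not supply. Under the assumed settings, the false-positive rate of the pooled exact test runs from no inflation to 97%. The higher figures need wide differences in both prevalence and toxicity that line up across trials, so neither 49% nor 97% should be read as the plan's actual error rate. Section 1.9 cites 10% to 30% smoking at diagnosis among cancer patients generally, which makes the wider prevalence range conceivable but does not establish it for these eight trials.

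Nothing here touches the IDFS comparison or any other randomized comparison in this trial. Severity is low, but the problem goes beyond missing detail: stratifying by parent trial is a better method than the one named, and it uses information already recorded.

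**What to change.** State in Appendix VI that tobacco-use and environmental-exposure comparisons are stratified by parent trial:

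- worst grade and reasons for discontinuation: Cochran-Mantel-Haenszel, van Elteren (for ordered grade) or stratified exact tests;
- time to discontinuation: stratified Gray's test;
- trial endpoints: stratified log-rank for any endpoint that is pooled, with a statement of which endpoints are pooled and which are analysed within trial;
- dose modification and relative dose intensity: a parent-trial term in the logistic models.

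Treatment arm may be added for precision. The consistency check should stay, as a supplement.

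The cost is a few sentences of analysis wording, with no new data or patients. Because the ancillary plan is embedded in several parent protocols, the wording has to be agreed for the ancillary as a whole and not in this protocol alone.

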2.3 Secondary Correlative Biomarker Objectives

- 2.3.1 To evaluate the association of genomic alterations identified via profiling of the surgical tumor specimen with RFS in patients with TNBC after neoadjuvant chemotherapy.
- 2.3.2 To explore whether any of the genomic alterations identified via profiling of the surgical tumor specimen can predict treatment benefit in patients with basal-like TNBC.
- 2.3.3 To determine the frequency of CTC positivity at baseline and after completion of study therapy in patients with TNBC with residual basal-like disease after neoadjuvant chemotherapy.
- 2.3.4 To evaluate the associations between CTC levels at baseline, and after completion of chemotherapy, with RFS

- 2.3.5 To evaluate the association between CTC change in status post-treatment (i.e. negative to negative, negative to positive, positive to negative, positive to positive) and RFS.
- Rev. Add8 2.3.6 To explore significance of CTC number/phenotype in predicting RFS.
- Rev. Add7 2.4 Exploratory Correlative Biomarker Objectives
- 2.4.1 To determine the frequency of plasma tumor cell-free DNA (cfDNA) positivity at baseline and after completion of study therapy in patients with TNBC with residual basal-like disease after neoadjuvant chemotherapy.
- 2.4.2 To evaluate the associations between plasma tumor cfDNA tumor-specific mutations (baseline and after therapy) with RFS.
- 2.4.3 To explore optimal biomarker combination for RFS prediction.
- Rev. Add#5 2.5 Exploratory Tobacco Use Objectives
- 2.5.1 To determine the effects of tobacco, operationalized as combustible tobacco (1a), other forms of tobacco (1b), and environmental tobacco exposure (ETS) (1c) on provider-reported cancer-treatment toxicity (adverse events (both clinical and hematologic) and dose modifications).
- 2.5.2 To determine the effects of tobacco on patient-reported physical symptoms and psychological symptoms.
- 2.5.3 To examine quitting behaviors and behavioral counseling/support and cessation medication utilization.
- 2.5.4 To explore the effect of tobacco use and exposure on treatment duration, relative dose intensity, and therapeutic benefit.
- NOTE:** Tobacco Use objectives described above are ancillary for the Tobacco Use Assessment project approved by NCI. A combined analysis of the data from the selected ECOG-ACRIN trials is planned. Data collected from the tobacco use assessment in each parent study will not be analyzed and reported in the clinical study report.

Rev. 9/17 3.

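### The tobacco ancillary's second-hand-smoke comparisons do not account for the patient's own smoking, so an active-smoking effect can appear as an environmental-exposure effect

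*Combined protocol and SAP*

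**What the plan says.** Section 2.5.1 lists three exposures separately. The aim is "To determine the effects of tobacco, operationalized as combustible tobacco (1a), other forms of tobacco (1b), and environmental tobacco exposure (ETS) (1c") on toxicity, meaning adverse events and dose modifications.

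Appendix VI, item 1, defines the variables. Own smoking is three-level: "smoking status (never smoker, former smoker, and current smoker based on Baseline STU Qs 1 and 5"). Second-hand exposure is a different variable: at baseline "environmental tobacco smoke (ETS) level (1c) will be determined by current household and work exposure (Baseline STU Qs 15-16"), and at follow-up "ETS level (1c) will be determined by 30 day household and work exposure (Follow-up STU Qs 11-12"). Own smoking plays no part in the ETS definition.

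Item 2 sets the outcome: "We will determine each patient's worst degree toxicity across all event types and treatment visits". It then compares the grade distribution "between smokers and non-smokers and between patients with environmental tobacco exposure and those without exposure using exact tests". For other products it adds: "We will also examine the distribution of worst degree grades between users with different form of tobacco use". Dose modification is to be analysed by logistic regression on tobacco use, with no covariates named.

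Item 5 compares treatment duration between smokers and non-smokers and "between patients with environmental tobacco exposure and those without exposure", using cumulative incidence and Gray's test. Reasons for discontinuation get exact tests. Relative dose intensity gets logistic regression on tobacco use and exposure, again with no covariates named.

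The opening of the statistical section adds only that consistency of effects across the eight parent trials would be examined.

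**The concern.** The objectives treat ETS (1c) as an exposure distinct from the patient's own smoking (1a). The ETS contrasts in items 2 and 5 do not keep the two apart. A patient who smokes and lives or works with other smokers falls in the ETS-exposed group, and nothing in Appendix VI removes her from the comparison or matches her with another smoker.

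Two conditions turn this into bias. First, smokers must have more household or work exposure than non-smokers. That is plausible, but the documents give no figure. Second, active smoking must affect toxicity. The introduction to Appendix VI asserts this qualitatively when it lists more treatment complications, including those of chemotherapy, among the risks of continued smoking. If both hold, the ETS-exposed group is enriched with smokers and shows more toxicity even when ETS does nothing. A finding credited to second-hand smoke could then be a repeat of the smoking finding.

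**Working it through.** **The plan's own figure.** The only power statement in Appendix VI is 83%, for a depression score in 26 quitters and 230 continuing smokers (difference 2.5, SD 4.08, 5% level). The standard error is 4.08 × √(1/26 + 1/230) = 0.844, and 2.5/0.844 = 2.96. Power is Φ(2.96 − 1.96) = 84% by the normal approximation and 83.9% by the noncentral t. The figure reproduces, but it does not concern ETS. No power or error rate is given for any ETS comparison.

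**Inputs from the plan (Appendix VI, item 3).** N = 1,500 with 20% smokers, so 300 smokers and 1,200 non-smokers.

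**Assumptions (not in the documents).** ETS prevalence e_S in smokers and e_N in non-smokers: 40/15%, 60/15% or 70/10%. Grade 3+ toxicity: 40% in non-smokers and 50% or 55% in smokers. True ETS effect: zero. Exposure is taken at baseline, non-smokers are treated as one homogeneous group, and worst grade is reduced to grade 3+ yes/no.

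**Formulas.**
- Smoker share among exposed: 0.2e_S / (0.2e_S + 0.8e_N).
- Smoker share among unexposed: 0.2(1 − e_S) / [0.2(1 − e_S) + 0.8(1 − e_N)].
- False ETS difference: (difference between these shares) × (smoking effect on toxicity).
- Rejection rate: Φ(d/SE − 1.96) + Φ(−d/SE − 1.96), with SE = √[p_E(1 − p_E)/n_E + p_U(1 − p_U)/n_U].

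| e_S / e_N | Exposed / unexposed n | Smoker share, exposed / unexposed | False difference, 40→50% | Rejection | False difference, 40→55% | Rejection |
|---|---|---|---|---|---|---|
| 40 / 15% | 300 / 1,200 | 40% / 15% | 2.5 points | 12% | 3.75 points | 22% |
| 60 / 15% | 360 / 1,140 | 50% / 10.5% | 3.9 points | 26% | 5.9 points | 50% |
| 70 / 10% | 330 / 1,170 | 64% / 7.7% | 5.6 points | 44% | 8.4 points | 77% |

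First row written out for 40→50%: exposed 0.4 × 50% + 0.6 × 40% = 44.0%; unexposed 0.15 × 50% + 0.85 × 40% = 41.5%; d = 2.5 points; SE = 3.2 points; d/SE = 0.78; rejection 12%.

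**Null checks.** With ETS prevalence of 20% in both groups, smokers are 20% of exposed and of unexposed, d = 0 and the rejection rate is about 5%. Simulated Fisher tests limited to non-smokers reject in about 4-5% of runs in every scenario. Simulated Fisher tests on all patients agree with the table within about 2 points.

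**Sensitivity to the assumptions.** With a 30% base rate, smokers at 40-50%, and ETS prevalences from 40 vs 20% to 70 vs 10%, simulated Fisher tests reject in 8% to 96% of runs. The direction is stable; the size depends on the inputs.

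**The case against.** The strongest reply is about scope. The tobacco objectives are headed exploratory, the analysis pools eight trials, and Section 2.5 says the data will not be reported in this trial's study report. No decision in this trial rests on the ETS test. That stands, and it limits the weight of the point. It does not repair a contrast that fails to isolate the exposure it names.

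The second reply is that the size is assumed. That also stands: the documents give neither ETS prevalence nor toxicity by smoking status, so the rates are illustrative.

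Third, the dose-modification and relative-dose-intensity models could include smoking status. They could, but the plan does not say so, and the exact tests and Gray's test as described have no place for it.

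Three stronger readings are tempting, and the documents do not support them:
- A reader might infer that the ETS test turns significant whenever smoking matters. In the lowest scenario above it stays non-significant 88% of the time, and with equal ETS prevalence there is no distortion.
- A reader might infer that the effect of other tobacco forms (1b) cannot be estimated at all. Only the worst-grade comparison is worded as among users; the logistic regressions on tobacco use are not confined to users, and non-users are in the data.
- A reader might infer that never and former smokers are merged. Item 1 defines three levels; items 2 and 5 then speak of smokers and non-smokers without saying where former smokers belong. That is an undefined term, not a stated merger.

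**Conclusion.** The concern holds in conditional form. As written, the ETS comparisons in items 2 and 5 take no account of own smoking, so an active-smoking effect can appear as an ETS effect. That all patients enter the comparison is read from the absence of any restriction; the plan does not say so in words. The bias needs unequal ETS prevalence by smoking status (assumed) and an effect of smoking on toxicity (asserted in the plan, size assumed). Under the illustrative inputs the false-positive rate is about 12% to 77% against a nominal 5%. This is a worthwhile correction to an exploratory pooled ancillary, with no bearing on the trial's IDFS, OS or PRO results.

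**What to change.** In Appendix VI, items 2 and 5, stratify every ETS comparison by never/former/current status: a stratified exact test for worst grade and for reasons for discontinuation, a stratified Gray's test for duration, and smoking status as a covariate in the logistic models. Alternatively, restrict the ETS comparisons to non-current smokers, preferably still separating never from former. State where former smokers fall in the two-group contrasts. As a minor addition, give the worst-grade comparison of other tobacco forms a non-user reference group.

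The survey items needed are already collected (Baseline Qs 1, 5, 7 and 14-16). Restriction leaves about 1,500 × 0.8 = 1,200 patients for the ETS test; stratification keeps all 1,500. The real cost is coordination: this is shared ancillary text, so the change must be made consistently across the parent trials and not in this protocol alone.
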